### **Dose Escalation**

For all MTDs (initial, subsequent and target doses), dose escalation will estimate the MTD. The estimated MTD is defined as the maximum dose at which fewer than

one-third of subjects experience a dose limiting toxicity (DLT) (minimum of 6 evaluable subjects for the target dose MTD; see Section 3.4 for definition of evaluable).

Dose Escalation will be conducted in two stages. In the single subject cohorts, single subjects will be enrolled at dose levels anticipated to be lower than those at which adverse events will be observed. Once higher dose levels are open for enrollment or when drug related safety or efficacy signals are observed (see below), the 3+3 design will be triggered.

Subjects who complete the DLT period (see Section 6.2.1.4) may proceed to a higher dose level for the following treatment cycle if no DLT has been reported for either this subject or any other subject in this dose cohort after completion of the DLT period, and once the next higher dose cohort is open for enrollment, after consultation with the sponsor (see Section 7.2.2 for details on assessments applicable in case of intra-subject dose escalation). DLTs experienced by subjects who proceeded to a higher dose as described above will not be considered for 3+3 decisions. However, the Dose Level Review Team (DLRT) may take this information into account to inform dose escalation recommendations.

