dosing intervals (EI) correspond to staying at the current dose (S). This study design uses a target toxicity level,  $p_T$  of 25%, and EI of (20%, 30%).

Decision rules are based on the unit probability mass (UPM) calculated on these equal-length intervals. Given an interval and a probability distribution, the UPM of that interval is defined as the probability of the interval divided by the length of the interval. If the interval with the largest UPM is from LI, EI or HI, then the corresponding dose decision would be E, S, or D, respectively.

A dose level will be considered unsafe, with no additional subjects enrolled at that dose level, if it has an estimated 95% or more probability of exceeding the target DLT rate  $p_T$  (ie,  $P [DLT > p_T | \text{data}] > 95\%$ ) with at least 3 evaluable subjects treated and evaluated at that dose level.

After the escalation phase is completed, final DLT rates at each dose level will be estimated by isotonic regression (Ji et al, 2010). The MTD will be determined as the dose level with the DLT estimate closest to the target toxicity level of 25%. In the case of dose levels with estimated toxicity of equal distance (tied dose levels) from the target toxicity of 25%, the following approach will be used (Ji et al, 2010): among all tied dose levels the highest dose level with target toxicity  $\leq 25\%$  will be selected, unless all tied dose levels have estimated toxicity  $> 25\%$ , in which case the lowest dose level will be selected.

A DLT will be defined as any of the events described below occurring in a subject during the DLT window, unless clearly attributable to causes other than AMG 330. The DLT window will be 4 weeks, regardless of the length of the treatment cycle. The CTCAE will be used to assess toxicities/adverse events with the exception of cytokine release syndrome (see [Table 7](#) for grading of cytokine release syndrome).

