### DLT Evaluation

A subject is not DLT-evaluable if he/she drops out before completion of the DLT window for reasons other than an adverse event related to study drug **or the subject has not received IP treatment for at least 14 days at the target dose for a 3- or 4-week cycle or at least 7 days at a target dose for a 2-week cycle**. All available safety data for subjects who are not DLT evaluable will still be evaluated and considered in DLRM decisions. No dose escalation will occur unless at least 3 subjects have **been assessed as DLT evaluable**. Duration of a cycle might be extended and be different from the duration of the DLT window. For all cohorts, the DLT window may also be extended

retrospectively to assess events starting or persisting outside the window in case the DLT definition is time dependent (eg, in case of neutropenia, see below).

Any adverse event occurring outside the DLT window that is determined by the investigator to be possibly related to the investigational product, which is seen more frequently or is more severe than expected or is persistent despite appropriate management, can be determined to be a DLT upon unanimous decision by the DLRT after review of the adverse event and all available safety data.

Events listed below are to be considered as DLTs and exceptions when occurring in a subject during the DLT window unless clearly attributable to causes other than AMG 330 treatment:

- Any treatment-related death.
- Grade 4 neutropenia lasting  $\geq$  42 days from start of cycle in absence of evidence of active AML (in case of 3 or 4 weeks treatment cycles, the number of days would increase accordingly)
- Grade 3–5 non-hematologic toxicity not clearly resulting from the underlying leukemia EXCEPT:
  - Alopecia
  - Grade 3 fatigue, asthenia, fever, anorexia, or constipation
  - Grade 3 nausea, vomiting or diarrhea not requiring tube feeding, total parenteral nutrition, or requiring or prolonging hospitalization
  - Infection, bleeding, or other expected direct complication of cytopenias due to active underlying leukemia
  - Grade 3 infusion reaction, if successfully managed and which resolves within 72 hours
  - Grade 3 rash
  - Grade 3 or 4 tumor lysis syndrome if it is successfully managed clinically and resolves within 7 days without end-organ damage.

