5.4 Endpoints

Treatment-Emergent Adverse Event (TEAE)

Events categorized as Adverse Events (AEs) starting on or after first dose of investigational product as determined by "Did event start before first dose of investigational product (enter response based on earliest administration of [REDACTED]
[REDACTED], or AMG330, whichever occurred first)" equal to "No" or missing on the Events eCRF and up to 30 days after last administration of AMG330 or end of study date, whichever is earlier. Disease related events (DREs) will be included in the TEAE summary.

The severity of each adverse event will be graded using the CTCAE version 4.0. Adverse events will be coded using MedDRA. For CRS events, revised grading system will be used as per protocol ([Lee et al. 2014](#)).

Treatment-Related AE

A treatment-related AE is any treatment-emergent AE that per investigator review has a reasonable possibility of being caused by the investigational product.

Dose Limiting Toxicities (DLT)

DLT will be determined by "Is this event a Dose Limiting Toxicity (DLT)?" equal to "Yes" on the Events eCRF. Investigators will determine whether an adverse event qualifies as a DLT per protocol [Section 6.2.1.4](#).

Overall Response:

Overall response definitions are given below for different indications.

Group 1 in dose-escalation cohort / Group 4 (R/R AML)

Response is defined as any of the following:

Complete remission (CR), CR with incomplete recovery (CRI) or morphologic leukemia-free state (MLFS) (all according to Revised International Working Group [IWG] response criteria for AML), or CR with partial hematologic recovery (CRh).

Group 2 (MRD+ AML) (Primary)

Response is defined as CR without minimal residual disease (CRMRD-) or CRI without minimal residual disease (CRiMRD-). MRD- is defined as MRD threshold below 0.1% as per ELN recommendations ([Schuurhuis et al., 2018](#)).

Group 2 (MRD+ AML) (Exploratory)

Group 3 (MDS)

Response is defined as any of the following:

CR or marrow CR (all according to Revised IWG response criteria for MDS)

Group 5 and Group 1 in dose-expansion cohort (R/R AML)

Response is defined as any of the following: CRMRD-, CR, CRi, CRh, MLFS, PR.

Minimum Residual Disease (MRD) Response (All groups):

Minimum residual disease response is defined as MRD negative, indicating presence of leukemia cells to 0.1% or lower of white blood cells.

Duration of Response (DOR):

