9.6 Safety Analyses

9.6.1 Analyses of Primary Safety Endpoint(s)

Unless otherwise specified, statistical analyses on safety endpoints will be done using subjects from the Safety Analysis Set, which includes subjects that are enrolled and received at least 1 dose of AMG 330. Unless otherwise noted, treatment groups will be defined based on the planned doses for Cycle 1.

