9.6.2 Analyses of Dose Limiting Toxicities

The analysis of Dose limiting toxicities (DLT) will be based on the DLT Evaluable Analysis Set. A listing and summary of the subject incidence of dose limiting toxicities (DLT) will be provided.

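### The SAP counts DLTs from the investigator's eCRF flag by planned cycle 1 dose, so a DLT flagged after intra-subject escalation can be charged to the lower dose and a DLRT-declared DLT counts only if the flag is updated

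*SAP*

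**What the plan says.** **What counts as a DLT in the analysis.** SAP 5.4 reads: "DLT will be determined by 'Is this event a Dose Limiting Toxicity (DLT)?' equal to 'Yes' on the Events eCRF". It adds: "Investigators will determine whether an adverse event qualifies as a DLT per protocol" section 6.2.1.4.

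**What that protocol section contains.** A DLT is a listed event in the DLT window: "The DLT window will be 4 weeks, regardless of the length of the treatment cycle". Under DLT Evaluation the window may be extended retrospectively when a criterion is time-dependent. An event outside the window that the investigator considers possibly related, and that meets further conditions on frequency, severity or persistence, "can be determined to be a DLT upon unanimous decision by the DLRT after review of the adverse event and all available safety data".

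**Intra-subject escalation.** Protocol 3.1.1 (Dose Escalation) lets a subject move to a higher dose after completing the DLT period, and states: "DLTs experienced by subjects who proceeded to a higher dose as described above will not be considered for 3+3 decisions". The DLRT may still take such events into account. The Multiple Subject Cohorts text extends the day-6 confirmation of DLT occurrence to intra-subject escalation.

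**How DLTs are tabulated.** SAP 9.6.2 uses the DLT-evaluable set: "A listing and summary of the subject incidence of dose limiting toxicities (DLT) will be provided". SAP 9.6.1 sets the grouping for safety analyses, subject to any exception noted elsewhere: "treatment groups will be defined based on the planned doses for Cycle 1". SAP 9.6.2 notes none.

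**Where the window is and is not written.** SAP 7.1 restricts the 3+3 rule and the expansion suspension rule to DLTs in the window. The DLT summary (9.6.2), the isotonic DLT rates for Groups 2 and 3 (3.3) and the final MTD/RP2D estimate from all DLT-evaluable subjects (3.1) carry no window, cycle or dose-at-onset condition.

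**The concern.** The protocol and the SAP do not define the same set of DLTs. The protocol recognises two deciders, the investigator and the DLRT, and treats DLTs at an escalated dose as a separate class. The SAP recognises one flag and one dose label per subject.

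Two errors can follow, in opposite directions. A flagged DLT at a higher dose in a later cycle would be counted at the planned cycle 1 dose, which overstates toxicity there. A DLT declared by the DLRT would be absent if nobody changes the flag, which understates toxicity at the dose concerned. DLT incidence is part of the primary endpoint and MTD estimation is a primary objective. Cohorts are small enough for one event to matter, and the final tables need not match the counts on which doses were chosen.

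**Working it through.** **1. The plan's own figures.** SAP 3.2 gives the probability of at least one DLT for true rates of 10% to 33%. The formula is 1 − (1 − p)^n.

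- n = 3: 1 − 0.90³ = 27.1%; 1 − 0.67³ = 69.9%. Stated: 27-70%.
- n = 6: 1 − 0.90⁶ = 46.9%; 1 − 0.67⁶ = 91.0%. Stated: 47-91%.

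These reproduce. The issue is event definition and dose attribution, not a wrong figure.

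**2. Following a flagged DLT after escalation through the stated rules.**

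- The subject completes the DLT period at cycle 1 dose A, stays DLT-evaluable, and escalates to dose B.
- An event at B is flagged as a DLT on the eCRF. SAP 5.4 counts it.
- SAP 9.6.1 places the subject under planned cycle 1 dose A, and 9.6.2 makes no exception.
- The DLT is reported at A, although it occurred at B and protocol 3.1.1 excludes it from the 3+3 count.

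**3. Following a DLRT-declared DLT.** Protocol 6.2.1.4 makes the event a DLT by DLRT vote. SAP 5.4 reads only the eCRF item. Neither document states a step that carries the vote into the flag or the analysis data. DLRMs use unlocked snapshots (SAP 7.1), while the primary and final analyses use a locked database (SAP 7.2, 7.3). No reconciliation between them is described.

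**4. Size with 6 evaluable subjects.**

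- One extra DLT: 1/6 = 16.7% becomes 2/6 = 33.3%. The Group 1 MTD definition requires less than 33%. In the SAP's printed mTPI-2 table, n = 6 moves from E (1 DLT) to D (2 DLTs).
- One missed DLT gives the reverse.

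**5. Effect on the final MTD rule in SAP 3.3.** The counts at three ascending doses are invented for illustration. I assume isotonic regression on raw proportions weighted by subjects; the target is 25%.

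| Case | Counts | Isotonic rates | Selected dose |
|---|---|---|---|
| All DLTs counted | 0/6, 1/6, 3/9 | 0, 16.7%, 33.3% | 2 |
| One DLRT-declared DLT at dose 3 not flagged | 0/6, 1/6, 2/9 | 0, 16.7%, 22.2% | 3 |

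In the first row doses 2 and 3 are both 8.3 points from 25%, and the tie rule takes the one at or below 25%. In the second, dose 3 is 2.8 points away.

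For the opposite error, suppose 0/6, 1/6, 2/9 is correct, which selects dose 3. One post-escalation DLT charged to dose 2 gives 0/6, 2/6, 2/9. Because 33.3% exceeds 22.2%, the two doses are pooled: (2 + 2)/(6 + 9) = 4/15 = 26.7%. They tie, both above 25%, and the rule takes the lower, dose 2.

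This second case needs intra-subject escalation in a group that uses isotonic regression. The rule is written under Group 1, but protocol 7.2.2 and Table 12 footnote c refer to intra-subject escalation in MRD+ AML, and the footnote also in MDS.

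**The case against.** The strongest case is that the definition is sounder than it looks.

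- **The window is imported.** A reader might infer that the SAP has no DLT window. It does: SAP 5.4 points to protocol 6.2.1.4, and SAP 7.1 writes the window into two rules. Only a programmed check is missing. This objection stands.
- **Misattribution is conditional.** A reader might infer that post-escalation DLTs are routinely charged to the lower dose. Escalation follows completion of the DLT period, so a later event is a DLT under 6.2.1.4 only through retrospective extension or a DLRT decision, or reaches the table because the investigator ticks the box anyway. This stands, but protocol 3.1.1 foresees such DLTs and asks for DLT confirmation after intra-subject escalation.
- **Dose decisions are made elsewhere.** A reader might infer that escalation ran on wrong counts. Protocol 3.1.1 keeps post-escalation DLTs out of 3+3 decisions, and the DLRT works from cumulative data and knows its own declarations. Live Group 1 3+3 decisions are not exposed.
- **Silence is not proof.** A reader might infer that DLRT decisions never reach the eCRF. Investigators vote on the DLRT, protocol 12.3 provides consistency checks and queries, and SAP 8.2 defers data handling to a Data Management Plan that is not among the documents. One can say only that the SAP does not state the step.
- **Planned cycle 1 dose is the natural grouping** for a four-week endpoint. That is true for in-window events on the cycle 1 regimen, but not for an event at another dose.

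**Conclusion.** The concern holds in conditional form. As written, the SAP would place a flagged DLT after intra-subject escalation under the planned cycle 1 dose, and would omit a DLRT-declared DLT whose flag was not updated. The exposure is the primary-endpoint DLT table and the final DLT-rate and MTD estimates in SAP 3.1 and 3.3.

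The size is one event in a small denominator: 16.7% against 33.3% at n = 6, in either direction. The illustrations show that one such event can change the selected dose. They rest on invented counts and on weighted raw proportions; the documents give no frequency for either kind of event, so neither the likelihood nor the net direction of error can be stated.

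**What to change.** In SAP 5.4 and 9.6.2:

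1. For the cohort DLT rate and MTD estimation, count only DLTs that occurred on the cohort's assigned cycle 1 regimen within the DLT window, including any retrospective extension that protocol 6.2.1.4 allows, plus DLTs that the DLRT declares for that regimen.
2. List DLTs after intra-subject escalation separately, under the dose received at onset.
3. Reconcile eCRF DLT flags with DLRM minutes before each database lock, and keep the reconciliation as a listing.

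Do not use a rigid 28-day onset filter. Protocol 6.2.1.4 allows extension for events that start or persist outside the window when the criterion is time-dependent, and its grade 4 neutropenia criterion needs at least 42 days from start of cycle. A fixed filter could drop valid DLTs.

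The cost is SAP wording, derived variables for window status and dose at onset, and one listing. No dose rule changes. SAP section 10 already anticipates protocol Amendment 10, so the protocol text could be aligned then.

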#### **7.5.2.1 MRD Testing for Screening/Eligibility for Subjects in Group 2**

For subjects to be eligible for study participation in Group 2, bone marrow aspirate is required prior to enrollment to establish MRD status. Collection of bone marrow aspirate following local standard of care procedure for MRD testing is not expected to present any additional risk to the health, safety, and welfare of the subject. Screening for MRD will be conducted using an investigational diagnostic or validated local test/assay with a minimum  $10^{-3}$  sensitivity at a CLIA certified laboratory (for US only) agreed upon by the Sponsor as listed in [Table 15](#) (Section 7.3.9); local testing is sufficient for the enrollment decision, if the test result is from < 21 days from the start of treatment. Additional bone marrow aspirate from the first bone marrow pull is required to be sent for testing at central lab and retrospective analysis for all subjects enrolled in Group 2. Timing of sample collection is described in the Schedule of Activities.

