#### **7.5.2.2 MRD Testing During Treatment**

After treatment initiation, subsequent MRD sample collections for central lab testing may be taken at the same time as the bone marrow aspirate collections for disease response assessment as indicated in the Schedule of Assessments, which is based on the following guidelines:

- Group 1: For subjects that achieve peripheral blood blast counts during hematology assessment after completion of the first and/or second cycle of AMG 330, or when PI suspects a CR, bone marrow aspirates will be collected for MRD status determination alongside disease assessment prior to initiation of the subsequent cycle. For patients who achieve CRi, additional bone marrow samples will be taken upon count recovery for MRD[-]CR status determination. For patients with confirmed CR, additional bone marrow aspirates for MRD status determination will be collected every cycle thereafter or when clinically indicated, until blast counts in whole blood rise above 0% and/or subject shows signs of clinical progression.
- Group 2: Bone marrow aspirates for MRD status determination will be collected after completion of every cycle or when clinically indicated, until blast counts in whole blood rise above 0% and/or subject shows signs of clinical progression.

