2.1 Objectives and Endpoints

Primary Objectives:

- Evaluate the safety and tolerability of AMG 330 in adult subjects with relapsed/refractory AML, MRD+ AML and MDS
- Estimate the maximum tolerated dose (MTD) and/or a biologically active dose [eg, recommended phase 2 dose (RP2D)] of AMG 330 in adult with relapsed/refractory AML, MRD+AML and MDS

Secondary Objectives:

- Evaluate the pharmacokinetics (PK) of AMG 330
- Determine the formation of anti-AMG 330 antibodies
- Evaluate the anti-leukemia activity of AMG 330 by evaluating
 - the number and proportion of subjects who respond to treatment with AMG 330. Response is defined as any of the following: complete remission (CR), CR with incomplete recovery (CRi) or morphologic leukemia-free state (all according to Revised International Working Group [IWG] response criteria) or CR with partial hematologic recovery (CRh).
 - the number and proportion of subjects with MDS who respond to treatment with AMG 330. Response is defined as any of the following: CR or marrow CR (all according to Revised IWG response criteria).
 - the number and proportion of subjects with MRD-positive AML (Group 2) who respond to treatment with AMG 330. Response is defined as conversion from MRD+ status with 0.1% threshold to MRD- status

- the duration of response, event-free survival, time to response, and overall survival

Exploratory Objectives:

- Evaluate the protein, nucleic acid, and cellular biomarkers in blood and / or bone marrow, as applicable [eg, cytokines, lymphocyte subsets, minimal residual disease (MRD – Group 1 only), leukemic stem cells (LSCs)]
- Evaluate effects of genetic variations in and phenotype of cancer genes, including apoptotic markers, on adverse event profile and treatment response
- Evaluate mechanisms of resistance
- Evaluate potential measures of clinical benefit including number of blood products transfused and days of antibiotic treatment of infection
- Evaluate the relationship between AMG 330 exposure and response to treatment
- [REDACTED]
- [REDACTED]
- [REDACTED]
- Explore the additional thresholds of conversions to MRD- status in MRD+ AML subjects as an efficacy measure for AMG 330 treatment

Primary Endpoint:

- Safety: subject incidence and grade of adverse events (AEs) and dose limiting toxicities (DLTs)

Secondary Endpoints:

- Pharmacokinetic parameters: half-life, steady state concentration, volume of distribution and clearance of AMG 330
- Incidence of anti-AMG 330 antibody formation

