- Efficacy parameters for R/R AML: response rate (response defined as CR/CRi/morphologic leukemia-free state [per modified IWG criteria] or CRh), duration of response, time to response, event-free survival and overall survival (duration of response, event-free survival, and overall survival will only be measured in the expansion cohort)
- Efficacy parameters for MRD-positive AML: response rate (response defined as conversion from MRD+ status with 0.1% threshold to MRD-), time to response,

relapse-free survival, and overall survival (relapse-free survival and overall survival will only be measured in the expansion cohort)

- Efficacy parameters for MDS: response rate (response defined as CR or marrow complete remission [per International Working Group (IWG) standardized response criteria]), duration of response, time to response, event-free survival and overall survival (duration of response, event-free survival, and overall survival will only be measured in the expansion cohort)

Exploratory Endpoints:

- Depletion of LSCs
- MRD response
- Lymphocyte counts, cluster of differentiation (CD) 33+ monocytes and T cells, as well as T cell activation (including T cell subsets). Other immune subsets may also be examined
- [REDACTED]
- [REDACTED]
- [REDACTED]
- Changes in serum cytokine levels
- Frequency and severity of cytokine release syndrome (CRS) and other AEs following [REDACTED] premedication, and alternative dose step schedules of AMG330
- [REDACTED]

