9.5.2 Analyses of Secondary Efficacy Endpoint(s)

The proportion of subjects with an overall response ([Section 5.4](#)) with corresponding exact 80% and 95% Confidence Intervals will be calculated using the Clopper-Pearson method ([Clopper and Pearson, 1934](#)) by cohort. The proportion of subjects who are event-free at 6 months with corresponding exact 80% CI will be calculated using the Clopper-Pearson method. The proportion of subjects with MRD response at the 0.1% threshold and the 0.01% threshold amongst subjects in the Safety Analysis Set will be summarized by cohort.

Listings indicating time to response, duration of response (DOR), and event-free survival will be produced for responders for each indication separately. For subjects in dose expansion cohorts, Kaplan Meier curves may be presented for event-free survival and overall survival with estimates for rates and 80% CI at selected weeks. DOR and time to response will only be analyzed for subjects who achieved an overall response.

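### SAP 5.4 defines Group 2 response without requiring MRD positivity at baseline, so a subject who was centrally MRD-negative at entry could be counted as a responder

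*SAP*

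**What the plan says.** SAP 5.4, under Overall Response for Group 2 (Primary), gives the rule: "Response is defined as CR without minimal residual disease (CRMRD-) or CRI without minimal residual disease (CRiMRD". The threshold follows: "MRD- is defined as MRD threshold below 0.1% as per ELN recommendations". Neither sentence asks that the subject was MRD-positive before treatment.

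This is the definition that will be programmed. SAP 9.5.2 takes the response rate, with its exact 80% and 95% intervals, from Section 5.4. SAP Section 6 makes the Safety Analysis Set, all enrolled and dosed subjects, the default population.

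Elsewhere the plan asks for conversion. The SAP 2.1 secondary objective says: "Response is defined as conversion from MRD+ status with 0.1% threshold to MRD- status". The SAP 2.1 secondary endpoint says: "response rate (response defined as conversion from MRD+ status with 0.1% threshold to MRD-), time to response". Protocol 10.1.1 defines the endpoint the same way, and protocol 7.6 names the Group 2 response category as a change from positive to negative. SAP Section 10 lists the removal of duration of response for this group but not a changed response definition.

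On testing, protocol 7.5.2.1 says that "local testing is sufficient for the enrollment decision" if the result is under 21 days old at the start of treatment. The central screening sample is mandatory for every enrolled Group 2 subject, but it is analysed retrospectively. On treatment, protocol 7.5.2.2 says: "subsequent MRD sample collections for central lab testing may be taken at the same time as the bone marrow aspirate collections".

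**The concern.** Inclusion criterion 4.1.8 admits Group 2 subjects who are already in CR or CRi. MRD status is therefore the only part of the 5.4 definition not already met at entry, and baseline MRD status is what separates a drug effect from no change. A subject who is positive on the local test and negative on the central one can be enrolled. If that subject stays in CR/CRi and the post-baseline central result is used, 5.4 is met even if nothing has changed.

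Two things are at stake. Assay disagreement would be counted as activity in the Group 2 response rate. A single such subject among the first 10 in expansion would also satisfy the minimum condition of one responder, on which the SAP's stopping probabilities are built.

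**Working it through.** **Inputs**
- The expansion condition is at least 1 responder in the first 10 (SAP 3.1).
- The stated stopping chances are above 59% for a response rate below 5% and below 11% for a rate above 20% (SAP 3.2; protocol 10.2).
- The stated 80% intervals at 20% response are 5.5% to 45.0% for n = 10 and 10.9% to 32.5% for n = 30, the latter with half-width 10.8 points (same sections).
- d is the share of subjects enrolled on a local positive result who are centrally negative at baseline and remain so in CR/CRi. The documents give no value; 2% to 20% is assumed.
- p is the true conversion rate among centrally MRD-positive subjects.

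**The plan's own figures reproduce.** P(no responder in 10) = (1 - rate)^10. This gives 0.95^10 = 59.9% and 0.80^10 = 10.7%. Clopper-Pearson 80% intervals are 5.5% to 45.0% for 2/10 and 10.9% to 32.5% for 6/30.

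**Effect of discordance under SAP 5.4, if central results are used after baseline**
- Apparent rate: q = d + (1 - d)p.
- Chance of at least one false responder in 10: 1 - (1 - d)^10. At p = 0 this is also the chance of meeting the 1-in-10 condition.
- Chance of no apparent responder in 10: (1 - q)^10.
- Bias in the conversion rate: q - p = d(1 - p).

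| Assumed d | At least 1 false responder in 10 | q at p = 5% | No apparent responder in 10, p = 5% | Bias at p = 20% (points) |
|---|---|---|---|---|
| 0% | 0% | 5.0% | 59.9% | 0 |
| 2% | 18.3% | 6.9% | 48.9% | 1.6 |
| 5% | 40.1% | 9.8% | 35.8% | 4.0 |
| 10% | 65.1% | 14.5% | 20.9% | 8.0 |
| 20% | 89.3% | 24.0% | 6.4% | 16.0 |

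One line worked through: at d = 10% and p = 20%, q = 0.10 + 0.90 x 0.20 = 0.28, and 0.28 - 0.20 = 8 points.

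**An illustrative result.** Suppose 6 of 30 are counted as responders and 3 of them were centrally negative at baseline. The reported rate is 20% (80% CI 10.9% to 32.5%). Counting the 3 as non-responders gives 3/30 = 10% (3.7% to 20.9%). Restricting to centrally MRD-positive subjects gives 3/27 = 11.1% (4.2% to 23.1%). The gap to the full-set rate is q - (1 - d)p = d. The gap to the rate among centrally positive subjects is d(1 - p).

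**The case against.** The strongest reply is that criterion 4.1.8 already requires MRD positivity at 0.1%. For a correctly classified subject, MRD-negative CR/CRi on treatment is conversion. On that view 5.4 is only loosely worded, and the open question is which assay governs, which would arise under the protocol definition too. That question does remain: restoring the word conversion alone would leave a local positive followed by a central negative open to being read as conversion. But it does not rescue 5.4, which sets no baseline condition on any assay.

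Several stronger readings are tempting, and the documents do not support them.
- A reader might infer that the SAP has abandoned conversion. It has not: SAP 2.1 keeps it, so this is an internal contradiction.
- A reader might infer that a local baseline will be paired with a central follow-up. Protocol Table 12, footnote f, requires both local and central MRD for Group 2 in cycle 1, so a same-assay comparison is available. Protocol 7.7 assigns MRD to central laboratories but treatment-response assessments to local ones. The artefact does not arise if local results govern throughout, or if central results govern at both times and conversion is applied.
- A reader might infer that no governing rule exists. Parts of protocol 7.5.2 and 7.6 are redacted, so only the readable text can be called silent.
- A reader might infer that one false responder opens expansion. Under protocol 3.1.5 and 10.3.2 and SAP 7.1, the Dose Level Review Team still decides on all cumulative data.

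Protocol 10.4.3.2 also calls the efficacy analyses exploratory. That limits the consequence, not the contradiction.

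**Conclusion.** The point holds as a defect in the operative definition. SAP 5.4 can count a subject who was centrally MRD-negative at baseline as a responder. It conflicts with SAP 2.1 and protocol 7.6 and 10.1.1, and the difference is undeclared.

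The size cannot be established. It depends on an unreported discordance rate, on central results being used after baseline, and on discordant subjects staying centrally negative in CR/CRi. Under an assumed d of 2% to 20%, the chance of at least one false responder in 10 is 18% to 89% at zero true conversion. At 5% true conversion, the chance of seeing no apparent responder in 10 falls from 59.9% to between 48.9% and 6.4%. A reader might put the bias in the conversion rate at a full 10 points for d = 10%, but d(1 - p) reaches that only at p = 0; at p = 20% it is 8 points. The endpoint is secondary and descriptive, but it feeds the expansion decision.

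**What to change.** In SAP 5.4, restore conversion for Group 2: baseline MRD at or above 0.1% and post-baseline MRD below 0.1%, in CR/CRi, both on the same assay. Name the central assay, since its screening sample is already collected for every Group 2 subject.

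- In the Safety Analysis Set rate, count subjects with a centrally negative or missing baseline as non-responders.
- Add a supportive rate restricted to centrally MRD-positive subjects.
- List the local/central discordant cases.
- Declare the definition in SAP Section 10 and align it with SAP 2.1.

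The cost is SAP wording and a slightly smaller denominator for the supportive rate. No new sampling is needed.
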